8.1.3 Safety

Safety of the treatment will be evaluated by adverse events, laboratory tests, vital signs, ECGs, performance status, and ophthalmic and dermatological evaluations.

All patients who received any amount of treatment will be included in the safety evaluation.

8.2 Statistical and Analytical Methods

8.2.1 Statistical Model

No statistical model will be used in the efficacy analysis and no formal hypothesis testing is planned. Descriptive statistics will be used to summarize the clinical activity, pharmacokinetics, and PD effect of vemurafenib and cobimetinib as described in the section on study objectives.

DLTs that occur in the first 28 days after initial dose of vemurafenib and cobimetinib will be used to determine the recommended dose. Subsequent DLTs will be reported and summarized as well.

The safety and efficacy (e.g., ORR, duration of response) will be presented by assigned dose cohort in the dose escalation stage and treatment group (patients previously treated with vemurafenib; patients previously untreated or treated [but without prior exposure to any BRAF or MEK inhibitor therapy] for locally advanced/unresectable or metastatic disease) in the dose expansion stage. The final analysis will be performed on all patient data collected through the 28 days after last patient's last dose of study drug or at least 12 months after last patient in, whichever occurs later. For all patients who completed 6 months SCC follow-up after end of treatment prior to protocol amendment j, an additional analysis will be performed to summarize any SCC findings per the RMP.

8.2.2 Hypothesis Testing

Descriptive statistical analyses will be performed for all analyses. Any statistical testing performed will be exploratory in nature and will be used to demonstrate the mechanism of action of vemurafenib and cobimetinib.

8.2.3 Analysis Populations

The treated population is defined as all patients who receive any amount of study medication. All safety analyses will use the treated population. Patients who enroll in the dose escalation stage who complete the DLT assessment window (Day 28) or experience a DLT in the assessment window and are withdrawn from study will be evaluable for determination of the recommended dose.

8.2.4 Safety Data Analyses

Safety will be assessed through summaries of DLTs, adverse events, changes in laboratory test results, changes in vital signs, and vemurafenib and cobimetinib exposures. Descriptive statistics will be used to summarize all safety data. Summary tables and listings will be presented by assigned dose cohort.

Adverse event data will be reported in listings and presented in frequency tables by Medical Dictionary for Regulatory Affairs (MedDRA) terms. All adverse events occurring on or after treatment on Cycle 1, Day 1 will be summarized. Summaries of adverse event by grade, seriousness, and relationship to study treatment will be presented, as well as summaries of adverse events leading to death or to premature withdrawal from study treatment. Serious adverse events, including deaths, will be listed separately and summarized.

Relevant laboratory and vital signs (temperature, heart rate, and blood pressure) data will be presented using summary statistics.

Laboratory data will be presented as summary tables for worst toxicity grade compared with baseline using Standard Internationale units. Descriptive statistics will be used to summarize ECOG performance status. Vital signs, ECGs, and ophthalmologic and dermatologic test results will be reported in the listings.

Exposure to study medication will be summarized by total duration of study medication, number of cycles started, and cumulative dose using descriptive statistics. Dose interruptions/modifications and their reasons will be presented.

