Cohort 1A (Figure 5) will test the safety and tolerability of vemurafenib at a dose of 720 mg bid in combination with cobimetinib at 60 mg/day on a 21/7 day schedule. Cohorts 1B and 1C may enroll patients only after the Cohort 1A dose combination is declared safe and tolerable. Cohort 1B will test the safety and tolerability of vemurafenib at a dose of 960 mg bid in combination with cobimetinib at 60 mg/day on a 21/7 day schedule, and Cohort 1C will test the safety and tolerability of vemurafenib at a dose of 720 mg bid and cobimetinib at 60 mg/day on a continuous schedule. After both Cohorts 1B and 1C are deemed to be acceptably safe and tolerable, Cohort 1D will open to evaluate the combination of vemurafenib at a dose of 960 mg bid and cobimetinib at 60 mg/day on a continuous schedule.

There will be no inpatient dose escalation during the DLT assessment window (Cycle 1, Days 1–28). After the DLT assessment window (Cycle 2 and beyond), patients without evidence of melanoma progression may receive cobimetinib at the highest cohort dose level for which there are at least 4 weeks of safety data demonstrating acceptable tolerability (i.e., no DLTs observed in a cohort of 3 evaluable patients or ≤ 1 DLT in a cohort of 6 evaluable patients). In some cases, this may allow the skipping of more than one dose level. For example, after Cohort 2A is determined to be safe and tolerable, patients in Cohort 2 may increase their daily dose of cobimetinib from 80 to 100 mg on a 14/14 schedule, and patients in Cohort 1 may increase their daily dose of cobimetinib from 60 to 100 mg on a 14/14 schedule. Patients that are beyond the Cycle 1 DLT assessment window are eligible for multiple, step-wise dose escalations (with agreement of the Sponsor's Medical Monitor) although dose escalations for an individual patient may not continue once that patient develops cobimetinib-related Grade ≥ 3 toxicity. Inpatient dose modification will be allowed in patients within a given cobimetinib administration schedule once the next higher dose level(s) is deemed to be acceptably safe and tolerable. Patients treated on a 14/14 schedule cannot transition to a 21/7 or a continuous daily schedule.

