This committee will review available relevant data on demographics, adverse events, laboratory assessments, 12-lead ECGs, and dose administration logs, as well as PK data. On the basis of a review of these data and in consultation with the participating investigators, a determination will be made as to whether dose escalation should continue, and if so, at what level and schedule. The selection of a recommended Phase II dose and schedule will depend upon results of the safety, activity, and PK evaluations from all patients treated in both the dose-escalation and cohort-expansion stages.

The overall vemurafenib and cobimetinib dose-escalation/de-escalation plan is depicted in [Figure 4](#), [Figure 5](#), [Table 5](#), [Table 6](#), and [Table 7](#).

On the basis of a review of available safety and PK data during this and other studies with both agents, dose-escalation may be halted or modified by the Sponsor, in consultation with investigators as deemed appropriate for safety concerns.

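### Escalation-stage tables by assigned dose cohort mix time before and after intrapatient escalation or permanent loss of one drug, and no planned output ties an event to the dose in effect

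*Combined protocol and SAP*

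**What the plan says.** - **Layout, safety.** Section 8.2.4 summarizes every adverse event from Cycle 1 Day 1 onward and worst-grade laboratory results: "Summary tables and listings will be presented by assigned dose cohort". It also plans exposure summaries and adds: "Dose interruptions/modifications and their reasons will be presented".
- **Layout, efficacy.** Under Section 8.2.1, safety and efficacy, with response rate and duration of response as examples, "will be presented by assigned dose cohort in the dose escalation stage and treatment group"; the treatment groups apply to the expansion stage.
- **Dose changes.** Section 3.1.1 bars intrapatient escalation (printed as inpatient) during Cycle 1. After that, patients without progression "may receive cobimetinib at the highest cohort dose level for which there are at least 4 weeks of safety data" showing acceptable tolerability, more than once if cleared. Vemurafenib may also rise from 720 to 960 mg bid in patients who tolerated 960 mg bid before the study. Escalations start on Day 1 of a cycle.
- **One drug only.** Section 3.1.6 lets some patients stay on one drug after permanent discontinuation of the other. Section 5.8 keeps patients on cobimetinib alone after progression in their assigned cohort, although they generally then take 60 mg on a 21/7 schedule.
- **Use.** Section 8.2.1: "DLTs that occur in the first 28 days after initial dose of vemurafenib and cobimetinib will be used to determine the recommended dose". Section 8.2.3 defines which escalation-stage patients "will be evaluable for determination of the recommended dose". Section 3.1.4 adds that selection of a dose and schedule "will depend upon results of the safety, activity, and PK evaluations from all patients treated in both the dose-escalation and cohort-expansion stages", and that the review committee sees "adverse events, laboratory assessments, 12-lead ECGs, and dose administration logs, as well as PK data".

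**The concern.** A column headed with a starting dose invites the reader to take its events as events on that dose. After Cycle 1 that need not be so. An adverse event or first response that arises at 100 mg cobimetinib is counted against 60 mg if the patient was assigned to Cohort 1. One that arises on cobimetinib alone is counted against the combination.

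This matters for one comparison in particular. Section 3.4 asks whether 14/14 dosing is better tolerated than 21/7 or continuous dosing, and Section 3.2 chooses expansion schedules from safety, activity and PK results by schedule. Table 5 provides matched starting doses for that question: Cohort 1 against 1A and 1C (720 mg bid with 60 mg), and Cohort 3 against 1B and 1D (960 mg bid with 60 mg). Only the 14/14 member of each set has a higher planned cobimetinib level on its own schedule, so the mixing is uneven across the columns being compared.

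**Working it through.** There is no stated figure to reproduce. The check is whether any planned output separates the time, and how far assigned and actual dose can diverge.

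**1. Does any output separate it?** Section 8.2.4 summarizes exposure and presents dose modifications, but neither is linked to the timing of events. Section 8.2.7.1 correlates PK parameters with dose, safety or efficacy, which is not a table of events by dose. The PFS and DOR censoring rules in Section 8.1.2 use the last evaluable tumor assessment and ignore dose or drug changes. Nothing is planned by dose received, before and after a change, or censored at a change.

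**2. Who is eligible for more cobimetinib?** In Table 5 the 14/14 levels are 60, 80 and 100 mg; all 21/7 and continuous cohorts use 60 mg.
- Higher level on the same schedule: Cohorts 1 (60), 2 (80), 3 (60) and 4 (80). None for 1A, 1B, 1C, 1D, 2A or 5.
- Patients: 4 × 3 = 12 to 4 × 6 = 24, of 10 × 3 = 30 to 10 × 6 = 60, or 40%, before any extra patients in cleared cohorts.
- Of the four, only Cohorts 1 and 2 start at 720 mg bid vemurafenib.
- Section 3.1.1 allows changes within a schedule once the next higher level is cleared. If that covers vemurafenib-only increases (1A to 1B, 1C to 1D), more cohorts are eligible.

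**3. How large is the gap?** Cobimetinib per 28-day cycle on 14/14 is 60 × 14 = 840 mg, 80 × 14 = 1,120 mg, 100 × 14 = 1,400 mg.
- 60 to 80 mg: 1,120/840 = 1.33 (+33%).
- 60 to 100 mg: 1,400/840 = 1.67 (+67%).
- 80 to 100 mg: 1,400/1,120 = 1.25 (+25%).
- Vemurafenib: 960/720 = 1.33 (+33%).
- Against Cohort 1A (60 × 21 = 1,260 mg per cycle), a Cohort 1 patient goes from 840/1,260 = 0.67 as assigned to 1,400/1,260 = 1.11 at 100 mg.

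**4. How early?** Upper bound, assuming instant enrollment and clearance: Cohort 1 clears after Cycle 1, Cohort 2 runs in that patient's Cycle 2, Cohort 2A in Cycle 3. So 80 mg is possible from Cycle 3 and 100 mg from Cycle 4. For N treated cycles (N is assumed):

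| N | Above 60 mg, (N−2)/N | At 100 mg, (N−3)/N |
|---|---|---|
| 4 | 2/4 = 50% | 1/4 = 25% |
| 6 | 4/6 = 67% | 3/6 = 50% |
| 12 | 10/12 = 83% | 9/12 = 75% |

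For Cohort 3, the 960/100 combination is tested only in Cohort 5, after Cohorts 2, 3 and 4 clear.

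**5. What can one patient do?** In a cohort of 3 to 6, one patient moves a rate by 1/6 = 17 to 1/3 = 33 percentage points.

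**6. Which direction?** Illustration only, all risks assumed. Take 13 cycles, a first-event risk of 2% per cycle at the assigned dose, and a change at Cycle 4.
- No change: 1 − 0.98^13 = 23%.
- Risk 1.5 times higher after escalation: 1 − 0.98^3 × 0.97^10 = 31%.
- Risk halved on one drug: 1 − 0.98^3 × 0.99^10 = 15%.

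Over changes at Cycle 2 to 7 and risk multipliers of 1.5 to 2, a 2% base risk gives 28–40% instead of 23%, and a 5% base risk 57–73% instead of 49%. With a halved risk the ranges are 13–17% and 30–38%. The mixing can push either way.

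**The case against.** **The case against.** No dose decision in Cycle 1 depends on these tables: the recommended dose rests on 28-day DLTs, escalation is barred in that window, and the committee sees dosing logs. The combination is already approved (Section 1.3.1) and DSMB monitoring has ceased after the Phase III analysis (Section 10). The four eligible cohorts are all 14/14, whereas the notes to Table 3 name 60 mg 21/7 as the proposed commercial cobimetinib regimen. Analyses are descriptive, tabulation by assigned cohort is a clear prespecified rule, and a determined reader could rebuild the split from listings and dose records. A censored table has its own selection problem, keeps time at reduced doses, and dose at onset is not always the causal dose: Section 3.10.1 places most cuSCC across the first 16 weeks.

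**What stands.** Most of this limits importance, and the limits are accepted. It does not show that the tables mean what their column headings suggest. Sections 3.1.4 and 3.2 do use later safety and activity data, and rebuilding by hand is not a planned output. The drawbacks of a censored table are reasons to print it beside the assigned-cohort table with a caveat, not to omit it. Table 12 also holds one drug temporarily while the other continues, so the censoring event must be permanent discontinuation, not any day on one drug.

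**Stronger readings that the documents do not support.**
- That the MTD or DLT findings are compromised: they are confined to Cycle 1.
- That lower-dose cohorts will look too toxic: escalated patients are non-progressors, and their escalation stops after cobimetinib-related Grade 3 or higher toxicity.
- That 40% of escalation patients took a higher dose: this is the share eligible, not the share escalated.
- That up to 83% of cycles could be at +67%: that share applies to any dose above 60 mg; for 100 mg the bound is 75%.

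**Conclusion.** The point holds as a matter of how the final cohort tables can be read. Escalation-stage adverse event, laboratory and response tables by assigned cohort include time after intrapatient escalation or after permanent loss of one drug, and nothing planned links an event to the dose in effect. Post-progression cobimetinib alone mainly affects the safety tables, since Section 5.8 does not require tumor forms after progression. Expansion-stage results, grouped by prior treatment, are outside the point.

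The scope is four cohorts on the narrower reading of Section 3.1.1, with a cobimetinib gap of 25% to 67% for those who escalate. The time bounds assume instant enrollment and clearance and 4, 6 or 12 treated cycles. How many patients escalated is not stated, so neither the size nor the net direction of any distortion can be computed. This is a worthwhile low-cost improvement, not a flaw in dose finding.

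**What to change.** Keep the assigned-cohort tables. Add to Section 8.2.4:

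> For the dose-escalation stage, adverse events and worst-grade laboratory results will also be summarized by assigned dose cohort with each patient censored at the first intrapatient dose escalation of either drug or, if earlier, at permanent discontinuation of one drug while the other continues (dated from the last dose of the discontinued drug). Temporary holds and dose reductions are not censoring events. The number of patients escalated and the cycles contributed will be shown per cohort, and the adverse event listing will show the dose of each drug in effect at onset.

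In the escalation-stage efficacy output, report how many responses were first documented after such a change. Beside the new table, state that follow-up is shorter and selected, that time at reduced doses remains in it, and that dose at onset need not be the causal dose for delayed events.

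A full cross-tabulation by dose received is not advised. Four vemurafenib levels (960, 720, 480, 240 mg) by five cobimetinib levels on 14/14 and three on each of 21/7 and continuous give 20 + 12 + 12 = 44 cells for 30–60 patients, and reductions would put patients selected for toxicity into the low-dose cells.

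**Cost.** One paragraph and modest programming. Dose modifications are already to be presented, and escalations start on Day 1 of a cycle, so that date is clear. The table keeps its 10 cohort columns. Section 18 says that a study report has been distributed; apply this only to the final analysis in Section 8.2.1, with nothing reissued.

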8.2.5 Exploratory Analyses

Pharmacogenetic Analysis

In order to explore the potential role of polymorphisms in drug metabolism enzyme and gene transporters in the PK disposition and safety profile of vemurafenib and cobimetinib, gene mutations may be assayed using multiplex PCR, allele-specific PCR, direct sequencing, or other appropriate methods. PK parameters, including dose-normalized AUC and C_{max} , would be compared between genotypes and, where possible, predicted phenotypes.

8.2.6 Determination of Maximal Tolerated Dose

Patients who withdraw from the study or who miss more than the allowed number of vemurafenib or cobimetinib doses prior to Cycle 1, Day 28 for reasons other than a DLT will be considered unevaluable for DLTs and will not be included in the determination of the MTD of the vemurafenib and cobimetinib combination. The MTD of the vemurafenib and cobimetinib combination will be determined according to the rules described in Section 3.1.4. In the event dose escalation does not continue until the MTD can be determined (e.g., because of PK futility), the MTD will be reported as “undetermined.”

8.2.7 Other Analyses

8.2.7.1 Pharmacokinetic Analysis

Several PK parameters derived from the blood PK samples will be analyzed using descriptive statistics (means, standard deviations, coefficients of variation, median). They will include C_{max} , C_{min} , and AUC. Additional parameters such as apparent CL, volume of distribution, and $t_{1/2}$ will be estimated if the concentration data are sufficient.

Estimation of the PK parameters will be performed using standard non-compartmental methods. Actual sampling times will be used to calculate PK parameters.

Steady-state pharmacokinetics of vemurafenib and cobimetinib will be summarized descriptively. Relevant PK parameters will be correlated with dose, safety, or efficacy variables.

8.2.7.2 Exploratory Biomarker Analyses

The aim of exploratory biomarker analyses is to explore the potential to predict efficacy (response, PFS, and survival) and/or toxicities by each marker separately and/or by suitable combinations.

Given the explorative nature of these analyses, no fixed analysis schedule can be specified. Exploratory analyses of individual biomarkers and combinations of markers will be conducted using appropriate statistical methods in a data-dependent way. The results might generate hypotheses on how biomarker observation could predict for benefit. Validation of the hypotheses will require a new set of independent data.

Additional biomarker data may become available from other studies prior to finalizing this study. Testing of biomarkers to support or confirm results from other studies will be specified in an analysis plan prior to closing this study.

FDG-PET response as defined by the EORTC will be used as a potential early readout of anti-tumor activity.

8.3 Sample Size

Design considerations were not made with regard to explicit power and type I errors but to obtain preliminary safety, PK, and PD information in this patient population. The number of patients expected to be treated with combination therapy in this two-stage study is approximately 130, assuming approximately 30–60 patients enroll in the dose-escalation stage (i.e., 10 dose cohorts) and at least 40 patients enroll in at least two expansion cohorts (one consisting of patients previously treated with vemurafenib, the other consisting of patients previously treated [but without prior exposure to BRAF or MEK inhibitor therapy] or previously untreated for locally advanced/unresectable or metastatic melanoma). This estimate does not include up to 20 patients who may enroll in the cobimetinib monotherapy cohort.

The sample size for this trial is based upon the dose-escalation rules described in [Table 13](#), which describes the properties of the dose-escalation rules with different underlying rates of DLT.

Patients who withdraw from the study prior to completing the DLT assessment window for reasons other than DLTs will be replaced.

Table 13 Properties of the Dose-Escalation Rules with Different Underlying Rates of DLT

Underlying Rates of Dose-Limiting Toxicity	Probability of Enrolling an Additional 3 Patients	Probability that the Dose Is Determined to be Tolerated
0.10	0.24	0.91
0.20	0.38	0.71
0.33	0.44	0.43
0.40	0.43	0.31
0.50	0.38	0.17
0.60	0.29	0.08

An expansion cohort of approximately 20 patients treated at the recommended dose will provide a reasonable chance (87.8%) of observing at least one or more adverse events when the true frequency of the adverse event is 10% at a given dose level. Table 14 provides probabilities of seeing at least one adverse event among 20 patients for probabilities ranging from 0.001 to 0.20 (i.e., adverse event frequencies of 0.1% to 20%). For example, if the true probability of an adverse event is 0.20 or greater, there is a more than an (98.8%) chance of seeing at least one such event in an expansion cohort of 20 patients.

Table 14 Probability of Safety-Signal Detection with an Expansion Cohort of 20 Patients

True Underlying Probability of an Adverse Event	Probability of Observing At Least One Adverse Event in 20 Patients
0.001	0.020
0.01	0.182
0.05	0.642
0.10	0.878
0.15	0.961
0.20	0.988

Preliminary evaluation of activity in the RAS/RAF-mutant population is an important study objective. With an expansion cohort of 20 patients RAS/RAF-mutant patients, if the true response rate is at least 20%, the chance of seeing at least one response is >98.8%.

9. DATA COLLECTION, MANAGEMENT, AND QUALITY ASSURANCE

The overall procedures for quality assurance of clinical study data are described in the Roche Standard Operational Procedures.

Data for this study will be recorded via an electronic data capture system using eCRFs and will be transcribed by the site from the paper source documents onto the eCRFs. **In no case is the eCRF to be considered as source data for this trial.**

Accurate and reliable data collection will be assured by verification and crosschecking of the eCRFs against the investigator's records by the study monitor (source document verification) and the maintenance of a drug-dispensing log by the investigator. Data management will be performed by [REDACTED] at the following address;

[REDACTED]

A comprehensive validation check program verifies that the data and discrepancy reports will be generated accordingly for resolution by the investigator.

